7.4. Time on Study

Duration of time on study in the PCP will be summarized, both as a continuous parameter (in units of days and weeks, as well as total number of subject-years) and as a categorical parameter as follows:

- PCP Week 12 Analysis
 - < 2 weeks, < 4 weeks, \geq 2 weeks, \geq 4 weeks, \geq 8 weeks, \geq 11 weeks, 2 days (which is the beginning of the protocol-specified visit window for the PCP Week 12 visit), \geq 12 weeks, and \geq 16 weeks
- PCP Final Analysis
 - The above categories for the PCP Week 12 Analysis through \geq 12 weeks inclusive, plus \geq 18 weeks, \geq 24 weeks, \geq 35 weeks, 2 days (which is the beginning of the protocol-specified visit window for the PCP Week 36 visit), \geq 36 weeks, \geq 39 weeks, 4 days (which is the beginning of the protocol-specified visit window for the PCP Week 40 Follow-up visit), and \geq 40 weeks

Other categories of duration of PCP time on study may be utilized for summary purposes as needed.

Duration of PCP time on study in days will be calculated as:

- PCP Week 12 Analysis:
 - For subjects who consent only to protocol version 1.0 and for subjects who consent to protocol version 2.0 and withdraw from PCP at or prior to PCP

Week 12: Date of last assessment in PCP – Date of first dose of PCP study treatment + 1

- For subjects who consent to protocol version 2.0 and do not withdraw from PCP at or prior to PCP Week 12: Date of PCP Week 12 nominal visit – Date of first dose of PCP study treatment + 1; if the date of PCP Week 12 nominal visit is missing, then time on study will be imputed to 85.
- PCP Final Analysis:
 - For subjects who are dosed in the OLE: Date of first dose of OLE study treatment – Date of first dose of PCP study treatment + 1
 - For subjects who are not dosed in the OLE: Date of last assessment in PCP – Date of first dose of PCP study treatment + 1.

Duration of PCP time on study will also be presented in a by-subject data listing.

8. EFFICACY EVALUATION

8.1. Overview of Efficacy Analysis Issues

8.1.1. Handling of Dropouts or Missing Data

The below approaches for handling of missing data will be applied after employing the approach for handling intercurrent events (ICEs) (ie, treatment failure rules) described in [Section 8.1.4](#) below.

8.1.1.1. Proportion-Based (Binary) Efficacy Endpoints

The primary analysis approach for handling of missing data for proportion-based (binary) efficacy endpoints will be non-responder imputation (NRI), wherein subjects with a missing value due to insufficient data for determination of endpoint status, including missing baseline value(s) and/or post-baseline value(s), will be considered as having not met the endpoint.

8.1.1.2. Change from Baseline (Continuous) Efficacy Endpoints

As all change from baseline (continuous) efficacy endpoints are exploratory endpoints, primary analyses of change from baseline efficacy endpoints will not employ imputation for missing data. Additional analyses of change from baseline efficacy endpoints (eg, mixed-effects model with repeated measures, methods utilizing imputation for missing data) may be explored.

8.1.2. Multicenter Studies

Data from all countries and sites will be pooled for the purpose of analyses.

8.1.3. Multiple Comparisons/Multiplicity

In general, statistical hypothesis testing for efficacy endpoints will be made without any adjustments for multiplicity, and all statistical hypothesis tests will be performed using a two-sided significance level of 0.050.

8.1.4. Handling of Intercurrent Events (Treatment Failure Rules)

For efficacy analyses, handling of intercurrent events (also known as treatment failure rules) will be applied as described below.

Subjects with any of the following ICEs that occur prior to the timepoint of the endpoint will be considered as not meeting the endpoint for proportion-based (binary) endpoints and as having missing values for change from baseline-based endpoints:

- Protocol-prohibited post-baseline initiation of a new UC rescue therapy medication
 - This includes post-baseline initiation of new UC rescue therapy medications such as systemic corticosteroids, azathioprine, 6-mercaptopurine, biologic therapies including anti-tumor necrosis factor agents or vedolizumab, tofacitinib, oral cyclosporine, sirolimus, mycophenolate mofetil, and per rectum therapy (eg, enemas or suppository formulations of steroids or 5-aminosalicylates) except those required for flexible sigmoidoscopy preparation. Use of systemic corticosteroids and per rectum therapy initiated post-baseline must be for > 3 consecutive days in order to qualify for this ICE.
 - This ICE is considered to have occurred on the first start date of new UC rescue therapy medication use.
- Protocol-prohibited post-baseline increase in a concomitant background UC therapy used at baseline (as described in [Protocol Section 6.5.2](#))
 - This includes the following:
 - Post-baseline increase of $\geq 20\%$ in the average total daily dose of concomitant background aminosalicylate UC treatment for ≥ 7 consecutive days, relative to the maximum total daily dose from 2 weeks prior to screening endoscopy up through and including the day prior to first dose of PCP study treatment (Day -1).
 - Post-baseline increase in the total daily dose of concomitant background systemic corticosteroid UC treatment for > 3 consecutive days, relative to the maximum total daily dose from 2 weeks prior to screening endoscopy up through and including the day prior to first dose of PCP study treatment (Day -1). Protocol-permitted increases in systemic corticosteroid dose up to baseline dose for a subject on systemic corticosteroids at baseline in whom systemic corticosteroid taper is initiated after PCP Week 12 and who cannot tolerate the systemic corticosteroid taper without recurrence of clinical symptoms of either UC or steroid withdrawal will not be considered an ICE.
 - This ICE is considered to have occurred on the first date of qualifying dose increase.
- Post-baseline prolonged course of systemic corticosteroids, where ‘prolonged’ is defined as consecutive use for > 7 days, for an indication other than UC.

This ICE is considered to have occurred on the first start date of qualifying systemic corticosteroid use.

- A colectomy (partial or total) or an ostomy.

This ICE is considered to have occurred on the procedure date for the colectomy or ostomy.

- Discontinuation of PCP study treatment > 28 days prior to the timepoint of the endpoint.

The approach for handling intercurrent events described above will be applied prior to employing the approaches for handling of missing data described in [Section 8.1.1](#) above.

Identification of ICEs may be performed by programmatic derivation and/or manual review. For the PCP Week 12 Analysis, this will be performed prior to Sponsor unblinding.

The number and percentage of subjects with an ICE will be summarized overall and by each of the types of ICEs listed above. For the PCP Final Analysis, this will be further summarized with respect to ICE occurrence prior to PCP Week 12. A by-subject data listing of ICEs will be provided.

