5.3. UC Disease Activity Criteria

Subjects meeting the following predefined UC Disease Activity criteria at or after the PCP Week 12 visit and prior to PCP Week 36 visit on IP may enter the OLE and receive GB004 BID treatment. Refer to [Table 8](#) for Mayo score calculation instructions in [Appendix 8](#).

- A Mayo score:
 - with Endoscopic subscore ≥ 2 using the centrally read endoscopy score from the flexible sigmoidoscopy,
 - AND
 - greater than or equal to the Mayo score at the PCP Day 1/Week 0 visit

AND

- Exclusion of other causes of disease activity unrelated to underlying UC (eg, infections), at the discretion of the Investigator

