8.3.4.1.2. Change from Baseline (Continuous) Exploratory Efficacy Endpoints

Change from baseline (continuous) exploratory endpoints will be analyzed using analysis of covariance (ANCOVA) models at all applicable timepoints based on application of ICE handling (where subjects with an ICE that occurs prior to the timepoint of the endpoint will be considered as having missing values as described in [Section 8.1.4](#)). All ANCOVA models will include covariates for treatment group, the randomization stratification factor of systemic corticosteroid use at baseline (yes/no), and baseline value corresponding to the change from baseline endpoint.

Descriptive statistics for change from baseline will be presented, along with the LS means, SEs, and corresponding 95% CIs for each treatment group from the ANCOVA models. The difference in LS means, SE, corresponding 95% CI, and p-value for each GB004 treatment group versus the placebo group from the ANCOVA models will also be presented.

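### Exploratory change-from-baseline analyses drop subjects after an intercurrent event and ignore their earlier visits, so Week 36 estimates can be biased if exits differ by arm

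*SAP*

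**What the plan says.** SAP 8.1.4 lists five kinds of ICE and calls the handling treatment failure rules: new UC rescue medication, an increase in background UC therapy, a prolonged steroid course for another indication, colectomy or ostomy, and stopping PCP treatment more than 28 days before the timepoint. A subject with such an event before the timepoint "will be considered as not meeting the endpoint for proportion-based (binary) endpoints and as having missing values for change from baseline-based endpoints".

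SAP 8.1.1.2 then states that "primary analyses of change from baseline efficacy endpoints will not employ imputation for missing data", giving as its reason: "As all change from baseline (continuous) efficacy endpoints are exploratory endpoints". SAP 8.3.4.1.2 fits ANCOVA at each timepoint, "where subjects with an ICE that occurs prior to the timepoint of the endpoint will be considered as having missing values". The covariates are treatment, steroid stratum and the baseline value. Alternatives are optional: "Additional analyses of change from baseline efficacy endpoints (eg, mixed-effects model with repeated measures, methods utilizing imputation for missing data) may be explored".

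Three other places bear on this:
- **Protocol 5.3.** Early OLE entry, at or after Week 12, needs a centrally read endoscopic subscore of at least 2 and a Mayo score "greater than or equal to the Mayo score at the PCP Day 1/Week 0 visit".
- **SAP 3.1.2.** For subjects dosed in the OLE, PCP data end at the first OLE dose.
- **SAP 8.3.3.** The optional hybrid imputation for primary and secondary endpoints assumes that ICE subjects are missing not at random (MNAR).

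**The concern.** One event is scored as failure on the binary endpoints but removes the subject from the continuous analysis at that timepoint. The ANCOVA conditions only on baseline information, so a poor Week 12 score that led to the exit plays no part in the Week 36 estimate. The SAP treats ICE subjects as MNAR in 8.3.3, and an available-case ANCOVA has no general protection from bias under that assumption.

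The endpoints at stake are Week 36 changes in Mayo, Modified Mayo and partial Mayo scores, Mayo subscores, RHI and UC-100. They will be reported with p-values and 95% CIs and could disagree with the binary results on the same scales. SAP Table 3 commits no sensitivity analysis for them, whereas the primary endpoint has four. The Sponsor is unblinded at the Week 12 Analysis, so an alternative for Week 36 chosen after that would be an unblinded choice.

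**Working it through.** **Inputs from the documents.** The only design calculation is for the binary primary endpoint: 10% vs 30.4%, two-sided 0.05, 80% power, 8% dropout. It reproduces. [1.96·√(2·0.202·0.798) + 0.842·√(0.10·0.90 + 0.304·0.696)]² / 0.204² gives 60 per arm, and 60/0.92 = 65.2, against about 65 stated. It supplies the 65 per arm used below. The documents give no ICE rates, SDs or mean changes for the continuous endpoints, so those are assumptions.

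**Step 1: ICEs that track the outcome.** Simulation with 65 per arm, residual SD 2.0, 4,000 runs per scenario, true difference -1.0, and ICEs more likely in subjects with worse outcomes:

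| ICE rate, placebo / GB004 | Planned ANCOVA |
|---|---|
| 8% / 8% | -1.00 |
| 20% / 20% | -1.00 |
| 15% / 5% | -0.78 |
| 5% / 15% | -1.23 |

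If ICEs depend only on baseline, the estimate is about -1.00 in every scenario. With no true effect, outcome-related ICEs at 15%/5% or 5%/15% produce a spurious mean difference of about 0.24 in absolute size, with opposite signs.

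**Step 2: exit driven by the Week 12 score, as in early OLE entry.** Assume mean changes of -1.5 (placebo) and -2.5 (GB004) at both visits, SD 2.0, and one exit threshold on the Week 12 change for both arms, set so that 18% of placebo leave.
- Placebo: z = 0.915. The mean Week 12 change in those who stay shifts by -2.0 × 0.2624/0.82 = -0.64.
- GB004: z = 0.915 + 1.0/2.0 = 1.415, so about 8% leave. The shift is -2.0 × 0.1465/0.922 = -0.32.
- The placebo stayers look better by a further 0.64 - 0.32 = 0.32 at Week 12. A fraction ρ, the assumed correlation between visits, carries over to Week 36.
- The available-case estimate is therefore -1.0 + 0.32ρ: about -0.90 at ρ = 0.3, -0.84 at 0.5 and -0.77 at 0.7.

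A separate illustrative simulation at 18% vs 8% gave -0.85 for the available-case ANCOVA and -1.00 for a two-visit likelihood analysis. The latter recovers the true value because the Week 12 score that drove the exit is in the model.

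**Step 3: scoring ICE subjects as zero change.** With mean changes of -1.5 and -2.5 in subjects without an ICE, the planned analysis gives -1.00 whatever the rates. The composite difference is (1 - f_A)(-2.5) - (1 - f_P)(-1.5), where f is the ICE rate:
- 8%/8%: -2.30 + 1.38 = -0.92
- 20%/20%: -2.00 + 1.20 = -0.80
- 15% placebo, 5% GB004: -2.375 + 1.275 = -1.10
- 5% placebo, 15% GB004: -2.125 + 1.425 = -0.70

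These gaps from -1.00 are differences between estimands, not biases.

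**The case against.** The SAP makes this choice openly and gives its reason: the endpoints are exploratory. It names the mixed model as a possible addition. Failure information is kept in the binary exploratory endpoints on the same scales, and ICEs are summarised by type and listed by subject. All of this stands and limits the importance of the point.

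Four stronger readings are tempting, and the documents do not support them.
- **That the estimates are biased.** The SAP states no estimand for these endpoints. Step 1 shows no mean bias with equal ICE rates or with missingness that depends only on baseline.
- **That placebo will look too good.** Nothing fixes which arm loses more subjects. Stopping PCP treatment counts whatever the reason, and Protocol 2.3.2 reports nausea in 18.8% on GB004 and none on placebo, although only one subject stopped for it.
- **That the ICE rule deletes the early OLE entrants' Week 36 values.** Most would have no such value, because SAP 3.1.2 ends their PCP data at the first OLE dose. Deletion of an observed value is a narrower case, such as a subject who stops treatment but stays in the PCP. The OLE argument does not apply to Week 12 change scores, since entry is possible only from Week 12.
- **That zero change is the right value.** Not every ICE is a UC failure; steroids for another indication are listed. The convention can also reverse a result: with -2.5 vs -3.0 in those who stay and exits of 20% placebo and 40% GB004, it gives 0.6 × (-3.0) - 0.8 × (-2.5) = +0.2.

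**Conclusion.** The point holds in limited form. The planned analysis uses an outcome-selected subset at Week 36 and discards the earlier visits that help explain the selection. It can be biased when outcome-related exits differ by arm. Under the assumed inputs the error is about 0.2 points on a true difference of 1.0, in either direction, and none with equal rates. This rests on assumed ICE rates of 5% to 20%, SD 2.0, mean changes of -1.5 and -2.5, and between-visit correlations of 0.3 to 0.7. Primary and secondary endpoints are binary, use ICE handling followed by non-responder imputation, and are unaffected. This is a cheap improvement, not a defect that threatens the trial's main conclusions.

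**What to change.** Amend SAP 8.1.1.2, 8.3.4.1.2 and Table 3 before the Sponsor is unblinded for the Week 12 Analysis:

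1. Make the mixed model for repeated measures the committed analysis for change-from-baseline endpoints with more than one post-baseline visit. Terms: treatment, visit, treatment-by-visit, steroid stratum and baseline value. Name the covariance structure, and say whether subjects who consented only to protocol version 1.0 contribute their early visits.
2. Keep the per-timepoint ANCOVA as a sensitivity analysis. It remains the main analysis where only one post-baseline visit exists, such as Mayo, Modified Mayo, RHI and UC-100 at the Week 12 Analysis.
3. Because SAP 8.3.3 treats ICE subjects as MNAR, pre-specify one Week 36 sensitivity analysis that keeps them with an unfavourable value, for example zero change or the last observed change if worse. Label it a composite strategy, not the primary estimate.

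If unblinding has already happened, record the choice before the PCP Final Analysis and report that it was made afterwards.

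Cost: SAP wording and slightly more programming. The mixed model relies on a missing-at-random assumption. For Mayo, Modified Mayo, RHI and UC-100 it has only Week 12 to draw on, so worsening after Week 12 is covered less well than for the partial Mayo score. The value in the sensitivity analysis is a convention.

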APPENDIX 6. PROHIBITED MEDICATIONS

The following medications are prohibited throughout the study:

- Azathioprine
- 6-mercaptopurine
- Any per rectum therapy (eg, enemas or suppository formulations of steroids or 5-aminosalicylates) except those required for flexible sigmoidoscopy preparation
- Marketed biologic therapies for any condition such as adalimumab, infliximab, vedolizumab, rituximab, golimumab, ustekinumab
- Tofacitinib, oral cyclosporine, sirolimus, mycophenolate mofetil
- Epoetin alfa
- Cholestyramine or other drugs interfering with enterohepatic circulation
- Any investigational agent other than GB004
- Chronic NSAID use (occasional use of NSAID, acetaminophen, or aspirin up to 325 mg/day is allowed)
- Anti-diarrheal medications (eg, loperamide, diphenoxylate/atropine)
- Strong CYP3A inhibitors and/or CYP3A inducers (eg, boceprevir, cobicistat, conivaptan, danoprevir, ritonavir, elvitegravir, grapefruit juice, indinavir, itraconazole, ketoconazole, lopinavir, paritaprevir, ombitasvir, dasabuvir, posaconazole, saquinavir, telaprevir, tipranavir, troleandomycin, voriconazole, clarithromycin, diltiazem, idelalisib, nefazodone, nelfinavir, carbamazepine, enzalutamide, mitotane, phenytoin, rifampin, St. John's wort)
- Inhibitors of UGT (eg, atazanavir; oral cannabidiol [≥ 5 mg/kg/day]; elbasvir and grazoprevir; encorafenib; epirubicin; oral fluconazole; fostamatinib; glecaprevir and pibrentasvir; isavuconazole; nelfinavir; ombitasvir and paritaprevir and ritonavir and dasabuvir; pazopanib; regorafenib; valproic acid).
- Dofetilide
- Sensitive CYP2C8 substrates (eg, repaglinide, rosiglitazone, pioglitazone, loperamide).

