For calculation of Partial Mayo score, 6-point Mayo score, PGA, SFS, and RBS Mayo subscores, and other applicable efficacy endpoints based on these scores at post-baseline analysis visits other than PCP Week 12 and PCP Week 36, the PGA closest to the target day will be used as the PGA subscore, and the corresponding PGA date will be used to determine the days of daily subject eDiary scores to be utilized for calculation of the SFS and RBS. If multiple PGA subscores are equally close to the target visit day, then the latest assessment will be utilized for calculation.

At each applicable analysis visit, SFS and RBS will each be calculated based on the average of the most recent 3 days with non-missing data within 14 days prior to the PGA date. If the PGA at a given visit is missing, then the date of another assessment at the given visit (eg, vital signs) may instead be used to determine the 14 day calculation timeframe. If the date for a given visit is completely missing, then the 14 day calculation timeframe may be determined relative to the target visit day. For the analysis visits of Baseline, PCP Week 12, and PCP Week 36, the day of and the day after flexible sigmoidoscopy/colonoscopy and the day(s) of bowel preparation, if performed, will be excluded from eligible days for calculation. Days selected for SFS and RBS calculation may be different based on eDiary data availability. SFS and RBS will be considered missing for subjects with fewer than 3 available days of eDiary data in the relevant calculation timeframe at a given visit.

Mayo scores and subscores will be presented in a by-subject data listing.

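### SAP 8.1.4 does not count repeated short steroid or rectal rescue, or rescue on the scored diary days, as treatment failure; the exposed cases are the last 28 days and subjects whose IP was not stopped

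*SAP*

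**What the plan says.** SAP 8.1.4 defines the intercurrent events (ICEs) that make a subject a failure. A subject with one before the timepoint "will be considered as not meeting the endpoint for proportion-based (binary) endpoints". For new UC rescue, most named agents have no minimum duration, but for two classes there is one: "Use of systemic corticosteroids and per rectum therapy initiated post-baseline must be for > 3 consecutive days in order to qualify for this ICE". For subjects already on steroids the event is: "Post-baseline increase in the total daily dose of concomitant background systemic corticosteroid UC treatment for > 3 consecutive days". A separate event covers stopping PCP treatment more than 28 days before the timepoint.

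The Protocol sets no such threshold. Section 6.5.2 bars starting new UC therapy up to the Week 36 visit. Section 7.1.5 requires permanent discontinuation of IP when new UC therapy is needed. Appendix 6 prohibits "Any per rectum therapy (eg, enemas or suppository formulations of steroids or 5-aminosalicylates) except those required for flexible sigmoidoscopy preparation".

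For the diary subscores, SAP 8.5.1 uses the "average of the most recent 3 days with non-missing data within 14 days prior to the PGA date". At the three visits with endoscopy (Baseline and Weeks 12 and 36) an exclusion applies: "the day of and the day after flexible sigmoidoscopy/colonoscopy and the day(s) of bowel preparation, if performed, will be excluded from eligible days for calculation". Rescue-medication days are not among those left out.

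**The concern.** A tolerance for brief use is reasonable, but this one is written on the length of a single run. It sets no limit on total days or on the number of courses, and it ignores where the use falls relative to scoring. The longest run that escapes, 3 days, equals the number of diary days averaged for SFS and RBS. A subject can therefore take prohibited therapy repeatedly near the timepoint, or on every scored day, and still be analysed as if the outcome were due to IP.

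No planned analysis tests this. In SAP Table 4, sensitivity analyses #1 and #3 drop ICE handling, and #2 and #4 keep the same definition. None is stricter. At stake is the attribution of remission and response in the primary and secondary comparisons.

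**Working it through.** **1. How much use can escape the rescue event.** A pattern of 3 days on and 1 day off never exceeds 3 consecutive days. Over 84 days to Week 12 it gives 84 × 3/4 = 63 treated days; over the last 28 days, 28 × 3/4 = 21. These are limits of the wording, not expected patterns.

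**2. What the discontinuation event already catches.** Take rectal therapy started at Week 4. If IP is stopped then, the stop is (12 − 4) × 7 = 56 days before Week 12. Since 56 > 28, the subject is a failure whatever the run length. If rescue starts within 28 days of the timepoint, this event cannot apply. If the site did not stop IP, it does not apply at any time. Section 7.1.5 speaks of new therapy and does not say whether an increase in an existing steroid triggers a stop.

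**3. Can a 3-day course cover the scored days?** Number days back from the PGA, assume a complete diary, place endoscopy g days before the PGA, and exclude the endoscopy day, the day after and, in the second case, one preparation day.

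| g | Scored days, no preparation day | Scored days, one preparation day |
|---|---|---|
| 0 | −1, −2, −3 | −2, −3, −4 |
| 1 | −2, −3, −4 | −3, −4, −5 |
| 2 | −3, −4, −5 | −4, −5, −6 |
| 3 | −1, −4, −5 | −1, −5, −6 |
| 4 | −1, −2, −5 | −1, −2, −6 |
| 5 to 12 | −1, −2, −3 | −1, −2, −3 |

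The scored days are consecutive except at g = 3 or 4, so in most layouts one 3-day course covers all of them without being an ICE. At g = 3 or 4 a single course cannot, although two shorter ones could.

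**4. Illustrative size.** SAP 2.6 gives 10% v 30.4%, about 65 per group, 8% dropout and two-sided 0.05. Evaluable n = 65 × 0.92 = 59.8. With p̄ the mean of the two rates, the pooled chi-squared approximation is

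power = Φ{[(p₁ − p₀)√n − 1.96√(2p̄(1 − p̄))] / √(p₀(1 − p₀) + p₁(1 − p₁))}.

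Design point: (0.204 × 7.733 − 1.96 × 0.5678)/0.5492 = 0.846, so power is 80.1%. The plan's figure of about 80% reproduces.

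Add k false remissions, each worth 1/59.8 = 1.67 percentage points:

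| k | Placebo only | Same k in both arms |
|---|---|---|
| 1 | 71.5% | 77.7% |
| 2 | 61.9% | 75.5% |
| 3 | 51.9% | 73.4% |

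Two on placebo and one on GB004 give 69.0%. One on GB004 alone gives 85.1%, an apparent gain that is bias in favour of GB004. With k/65 and n = 60 instead, placebo only gives 72.4%, 63.6% and 54.5%, and both arms 78.0%, 76.0% and 74.1%. The values of k are assumptions.

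**The case against.** The best defence is that the Protocol stops IP when new UC therapy is needed, so the discontinuation event catches early rescue. That stands, and it limits the point. A reader might infer that intermittent rescue at any time before Week 12 escapes; where Section 7.1.5 is followed, it does not.

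An every-other-day enema is also not clearly exempt. Protocol 6.8 records start date, end date and frequency, so one intermittent record could be flagged from its dates alone. The SAP does not say which derivation applies. Manual review of ICEs is allowed, but no criterion beyond the stated threshold is given.

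Three other stronger readings are tempting and not supported:

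- *A 3-day enema course creates a remitter.* Clinical remission also needs a centrally read endoscopic subscore of 0 or 1, and the documents do not say how far a short course changes endoscopy.
- *The diary argument reaches every secondary endpoint.* Endoscopic improvement, histologic remission and mucosal healing use no diary days. Only the repeated-course argument reaches them.
- *The error must dilute the treatment effect.* That assumes uncounted rescue falls mainly on placebo, which is plausible but nowhere documented.

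Short use would be visible in the medication and deviation listings (SAP 6.7 and 5.2). That helps a reader of the report but leaves the estimates unchanged.

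Finally, a cumulative limit of 3 days with no time horizon would fail a Week 36 remitter for four scattered days of use in 36 weeks. That objection is fair, and the fix below is bounded accordingly.

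**Conclusion.** The point holds within limits. The consecutive-day threshold leaves uncounted any steroid or rectal rescue, or background-steroid increase, in runs of 3 days or less during the last 28 days, and at any earlier time if IP was not stopped. Use on scored days is not addressed at all. Such subjects can count as clinical responders and, given an endoscopic subscore of 0 or 1, as remitters.

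The number of subjects and the direction of bias cannot be derived from the documents. If one to three subjects were affected, power at the design point would fall to between 71.5% and 51.9% when all are on placebo, and to between 77.7% and 73.4% when the arms are affected equally. An excess on GB004 would favour GB004. The rule should be amended, but this is not evidence that the primary result will be wrong.

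**What to change.** Amend SAP 8.1.4 before the Sponsor is unblinded for the Week 12 Analysis, which is also the last blinded opportunity for the Week 36 endpoints:

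1. For endpoints that use SFS or RBS, count any protocol-prohibited steroid or rectal UC therapy on a day selected for scoring as an ICE.
2. Within the 28 days before the timepoint, count such use as an ICE when it totals more than 3 days, consecutive or not. State that one intermittent-dosing record counts from its start to its stop date. Use the same wording for background-steroid increases, keeping the existing exception for protocol-permitted increases after a taper.
3. Add a sensitivity analysis of the primary and secondary endpoints that treats any protocol-prohibited UC rescue before the timepoint as failure, with a by-arm listing of use not counted under the primary rule. This covers earlier use where IP was not stopped, which item 2 does not reach.

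The 28-day limit meets the boundary of the discontinuation event and avoids failing subjects for scattered use months earlier. The data are already collected under Protocol 6.8. The cost is revised SAP wording and programming, one further sensitivity analysis and listing, and a few more non-responders in any arm.
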